9.1 Cumulative incidence of SARS-CoV-2 infection regardless of symptomatology

Analysis will be the same as for the primary endpoint COVID-19.

9.2 Cumulative incidence of asymptomatic, mild/moderate, and severe (requiring hospitalisation) SARS-CoV-2 infection.

Analysis will be the same as for the primary endpoint COVID-19.

9.3 Cumulative incidence of influenza infection

Analysis will be the same as for the primary endpoint COVID-19.

9.4 Cumulative incidence of RTI

Analysis will be the same as for the primary endpoint COVID-19.

9.5 Cumulative incidence of medically attended RTI

Analysis will be the same as for the primary endpoint COVID-19.

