4.3 Study definitions

COVID-19 disease is defined as respiratory tract symptoms and/or systemic symptoms in combination with detection of SARS-CoV-2 in a respiratory sample.

SARS-CoV-2: severe acute respiratory syndrome coronavirus-2. The virus that causes COVID-19 disease.

crRTI: clinical symptoms of a respiratory tract infection in combination with the need for medical intervention. (See protocol for a detailed definition.)

5 General statistical considerations

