7.1 Demographics / baseline characteristics

The following data will be described for included participants by treatment arm and for the total population:

VARIABLE	DERIVATION	STATISTICAL METHOD *
Age (years)	Self-reported at baseline	Median (IQR) or mean (sd) ¹
Gender	Self-reported at baseline: Male/ Female	n/N (%)
History of BCG vaccination	Self-reported at baseline: Yes/No	n/N (%)
Age at BCG vaccination	Self-reported at baseline	Median (IQR) or mean (sd) ¹ among those with reported history of BCG vaccination
BMI	Self-reported at baseline	Median (IQR) or mean (sd) ¹
Receipt of influenza vaccination in past season (2019-2020 or 2020-2021 depending on date of enrolment)	Self-reported at baseline: Yes/No	n/N (%)
Receipt of pneumococcal vaccination in past or current season	Self-reported at baseline: Yes/No	n/N (%)
Receipt of other vaccinations in past 12 months	Self-reported at baseline (open question) ²	n/N (%) for each reported vaccination
History of hypertension	Self-reported at baseline: Yes/No	n/N (%)
History of cardiovascular disease	Self-reported at baseline: Yes/No	n/N (%)
History of stroke	Self-reported at baseline: Yes/No	n/N (%)
History of diabetes mellitus	Self-reported at baseline: Yes/No	n/N (%)
History of COPD	Self-reported at baseline: Yes/No	n/N (%)
History of asthma	Self-reported at baseline: Yes/No	n/N (%)
History of other pulmonary diseases	Self-reported at baseline: Yes/No and open question ²	n/N (%) for each reported pulmonary disease if deemed relevant
History of moderate to severe renal disease	Self-reported at baseline: Yes/No	n/N (%)
History of solid organ or haematological malignancy	Self-reported at baseline: Yes/No	n/N (%)
History of dementia (diagnosed by physician)	Self-reported at baseline: Yes/No	n/N (%)
History of other chronic diseases	Self-reported at baseline: Yes/No and open question ²	n/N (%) for each reported disease if deemed relevant
Medication use	Self-reported at baseline	Listing of medication on group level based on ATC code system
Clinical Frailty Scale	Self-reported at baseline	Median (IQR)

History of smoking	Self-reported at baseline. Options are: - Never smoked - Ever smoked - Current smoking	n/N (%) for all categories
Smoking of household member	Self-reported at baseline: Yes/No	
Alcohol use	Self-reported at baseline: Yes/No, quantity in categories	n/N (%) per category
History of allergic rhinitis	Self-reported at baseline: Yes/No	n/N (%)

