The primary study parameter will be analyzed as a time-to-event outcome using a Cox proportional hazards analysis. The randomization date will be considered T=0 and the symptom onset date of the primary endpoint (or in case of COVID-19 the date of positive test result if that occurs earlier) will be considered the event time. Censoring time of participants with no event will be the last date of follow-up. The analysis will be adjusted for the stratification variables (hospital and age category) and for strong prognostic factors*. The result will be reported as the number of episodes per arm, number of patient-years of follow-up per arm, and hazard ratio (HR) with 95% CI.

* For COVID-19 there are no prognostic factors that can be measured at enrolment so only stratification variables will be used. For clinically relevant RTI: presence of the following (groups of) comorbidities: cardiovascular disease or stroke, chronic pulmonary disease (COPD, asthma or other chronic pulmonary disease), diabetes mellitus, solid organ or hematological malignancy, moderate to severe chronic renal disease.

9 Analysis of the secondary endpoints

Please refer to the protocol for definitions of each endpoint.

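### Sections 9.5 to 9.7 use the COVID-19 model and so leave out the comorbidities that section 8 names as strong prognostic factors for clinically relevant RTI: valid, but slightly inefficient and not matched to the crRTI analysis

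*SAP*

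**What the plan says.** SAP section 8 sets the model: "The primary study parameter will be analyzed as a time-to-event outcome using a Cox proportional hazards analysis". On covariates it says: "The analysis will be adjusted for the stratification variables (hospital and age category) and for strong prognostic factors". A footnote then gives a separate list for each candidate primary endpoint.

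- COVID-19: "For COVID-19 there are no prognostic factors that can be measured at enrolment so only stratification variables will be used".
- crRTI: "For clinically relevant RTI: presence of the following (groups of) comorbidities: cardiovascular disease or stroke, chronic pulmonary disease", followed by diabetes, malignancy and renal disease, which makes five groups.

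Section 4.3 describes the second endpoint as "crRTI: clinical symptoms of a respiratory tract infection in combination with the need for medical intervention" and leaves the detail to the protocol.

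Sections 9.5 (medically attended RTI), 9.6 (RTI-related admission) and 9.7 (pneumonia) each consist of one sentence: "Analysis will be the same as for the primary endpoint COVID-19". Section 9.4 (any RTI) has the same sentence.

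The baseline table in 7.1 collects all the comorbidities by self-report, for example "History of moderate to severe renal disease" and "History of solid organ or haematological malignancy".

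**The concern.** The cross-reference gives three RTI outcomes the shorter covariate list. Section 8 justifies that list by a statement about COVID-19 only. For the RTI candidate endpoint, the same footnote says that measurable strong predictors exist. Nothing elsewhere in the SAP restores the comorbidities for 9.5 to 9.7 or explains the choice.

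Two things are at stake, both small.

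- **Precision.** Leaving a prognostic covariate out of a Cox model moves the treatment HR towards 1 and costs some power, even in a randomised trial.
- **Comparability.** Under section 8, crRTI is analysed whichever candidate is selected, because the other becomes secondary. Its HR, adjusted for comorbidity by its own list, would stand beside HRs for closely related outcomes adjusted for less. Part of any difference between them would come from the model.

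**Working it through.** **1. Text side by side**

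| Endpoint | Covariates besides hospital and age category | Reason given |
|---|---|---|
| COVID-19 (section 8) | none | no predictor measurable at enrolment |
| crRTI (section 8) | five comorbidity groups | strong prognostic factors |
| 9.5, 9.6, 9.7 | none, by reference to COVID-19 | none |

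**2. The plan's own event numbers.** Section 3 gives 67 events for 80% power and 90 for 90% power, for a 50% reduction at two-sided 0.05, with 1:1 allocation (section 2). Schoenfeld's formula is 4(z₁₋α/₂ + z_power)² / (ln HR)².

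- 80%: 4 × (1.960 + 0.842)² / 0.4805 = 65.4, so 66.
- 90%: 4 × (1.960 + 1.282)² / 0.4805 = 87.5, so 88.

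Both are close to the stated figures. They use no covariates, so the point does not touch them.

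**3. Cost of leaving out the comorbidities.** The SAP gives no prevalences, comorbidity effects or secondary event counts. All of these are assumed:

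- prevalences 35, 20, 20, 15 and 12%;
- HR per comorbidity 1.2, 1.5 or 2.0;
- comorbidities independent, or mildly correlated (one-factor latent normal, correlation 0.3; pairwise phi 0.14 to 0.17);
- constant hazards, administrative censoring, hospital and age category not modelled.

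N is 5,200 to 7,000 (section 2). The large-sample limit of the Cox estimator without comorbidities, and the information of the model with them, were computed over the 2⁵ = 32 comorbidity strata. Power is Φ(|ln HR| / SE − 1.96).

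Worked case: 90 events, N = 5,200, correlated, comorbidity HR 2.0, true HR 0.500. SE is 0.2231 in both models, and the HR without comorbidities tends to 0.5047.

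- With comorbidities: 0.6931 / 0.2231 − 1.96 = 1.147, power 87.4%.
- Without: 0.6838 / 0.2231 − 1.96 = 1.105, power 86.5 to 86.6%.
- Loss: about 0.9 points.

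Both powers are below Schoenfeld's 90.8% at 90 events because this SE allows for the unequal split of events between arms. The SEs of the two models agree to within 0.0001 in every scenario, so the loss comes from the shift of the HR.

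Percentage points of power lost (independent / correlated; ranges cover N = 7,000 to 5,200):

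| Events (treatment HR) | comorbidity HR 1.2 | 1.5 | 2.0 |
|---|---|---|---|
| 90 (0.500) | <0.1 / <0.1 | 0.1 / 0.1–0.2 | 0.3–0.4 / 0.7–0.9 |
| 150 (0.625) | <0.1 / <0.1 | 0.1–0.2 / 0.3–0.4 | 0.5–0.7 / 1.3–1.8 |
| 300 (0.721) | 0.1 / 0.1 | 0.3–0.4 / 0.6–0.8 | 1.1–1.4 / 2.7–3.5 |
| 600 (0.795) | 0.1 / 0.2 | 0.6–0.8 / 1.2–1.6 | 2.1–2.8 / 5.1–6.6 |

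Above 90 events the treatment HR was set so that the adjusted model has 80% power. At 90 events, a true HR of 0.500 becomes at most 0.502 (independent) or 0.505 (correlated).

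**4. Check by simulation.** Paired Cox fits, N = 5,200, correlated, 1,500 replicates each, gave these gains from adjustment:

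- 90 events, comorbidity HR 1.5: +0.1 points (SE 0.3), against 0.2 above;
- 600 events, HR 1.5: +1.3 (SE 0.6), against 1.6;
- 600 events, HR 2.0: +6.1 (SE 0.8), against 6.6.

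The five extra parameters raised the mean SE of the log HR at 90 events only from 0.2260 to 0.2262.

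**The case against.** The strongest reply is that nothing here is wrong. The sentence on strong prognostic factors governs the primary parameter, and no section promises the same for secondary endpoints. Every time-to-event endpoint in section 9, mortality (9.10) included, points to the COVID-19 model. The functioning scores in 9.8 also use only the stratification variables. It looks like one simple, pre-specified rule. The five groups are named as prognostic for crRTI only, so carrying them to 9.5 to 9.7 is an inference. Without the protocol definitions, the overlap between medically attended RTI and crRTI cannot be judged.

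All of that stands, and it rules out several stronger readings.

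- **That the SAP contradicts itself.** It does not; the cross-references are clear.
- **That the results would be biased.** Randomisation protects the comparison. The HR not conditional on comorbidity is a different quantity, not a wrong one.
- **That much power is lost.** The larger figures rest on assumed event counts and on treatment HRs reset to give 80% power. At 1,500 events with correlated comorbidities of HR 2.0, the same calculation gives 10.8 to 13.2 points, but nothing in the SAP suggests such counts. Under the plan's own 50% reduction, Schoenfeld power at 150 events is already Φ(√150/2 × 0.6931 − 1.96) = 98.9%, so almost none could be lost. The SAP sets no power target for these endpoints.
- **That 9.4 is equally affected.** Predictors of needing medical intervention need not predict mild infection.

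The reply does not supply a reason for the shorter list. A preference for small models is not stated, and the plan accepts the five groups for crRTI at 90 episodes.

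**Conclusion.** The point holds as a minor matter of efficiency and consistency for 9.5 to 9.7. It is firmest for 9.5, which is closest to crRTI by name, and plausible for 9.6 and 9.7. The gain is real but small: under 1 point of power at about 90 events, and a few points only if events are several times as many and each comorbidity has a strong effect. These sizes depend on the assumed prevalences, comorbidity HRs and event counts, and outcomes rarer than 90 events were not examined. The primary endpoint and the event targets are unaffected. Confidence is medium, because the prognostic value of the five groups beyond crRTI is inferred.

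**What to change.** Before unblinding, change the cross-reference in 9.5 so that it names clinically relevant RTI instead of COVID-19. Do the same in 9.6 and 9.7 unless events are too few to support five more parameters; if so, say that in the SAP as the reason for the shorter list. Changing 9.4 is optional.

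The change is to SAP wording only, since the comorbidities are already collected. It has two downsides: five more parameters in each model, and possible multiple imputation under section 5.2 where self-reported comorbidities are missing. No measurable power gain should be expected at about 90 events. The redirection also drops the COVID-19 rule that an earlier positive test date counts as the event date, so the authors should confirm that symptom onset alone is intended for these endpoints.

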9.6 Cumulative incidence of RTI related hospital admission

Analysis will be the same as for the primary endpoint COVID-19.

9.7 Cumulative incidence of pneumonia diagnosed by a GP or medical specialist

Analysis will be the same as for the primary endpoint COVID-19.

9.8 Mental, physical and social functioning at 6 months

The change in Katz-Activities of Daily Living score, Lawton Activities of Daily Living score and EQ5D quality of life score between baseline and end of study will be analysed using linear regression. The stratification variables (hospital and age category) will be added as covariates to the model. The results will be reported as differences in change of score with 95% confidence intervals.

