Objective: To determine the impact of BCG vaccination on the incidence of clinically relevant respiratory infections or COVID-19 in vulnerable elderly.

Study design: An adaptive multi-center double-blind randomized placebo-controlled trial.

Study population: 5,200 to 7,000 vulnerable elderly, defined as ≥ 60 years of age and being discharged from hospital in the last 6 weeks, having a chronic somatic comorbidity, undergoing major surgery, or attending a thrombosis care service. Patients with contraindications to BCG vaccination as stipulated in the Summary of Product Characteristics (SPC) and patients with a history of COVID-19 will be excluded.

Intervention: Participants will be randomized between intracutaneous administration of BCG vaccine (Danish strain 1331) or placebo (0.1ml 0.9% NaCl) in a 1:1 ratio.

Main study parameters/endpoints: The trial has an adaptive primary endpoint. Based on accrual of the two endpoints, the primary endpoint will be either (a) COVID-19 or (b) clinically relevant respiratory tract infection (RTI) requiring medical intervention, potentially including COVID-19 episodes. The other will be declared secondary endpoint. Other secondary endpoints include: all SARS-CoV-2 infections (including asymptomatic infections), influenza infection, RTI (all infections regardless of medical intervention), RTI-related hospital admission, COVID-19 related hospital admission, pneumonia, mental, physical and social functioning, serious adverse events and adverse events, and death.

Nature and extent of the burden and risks associated with participation, benefit and group relatedness: Based on previous experience in published and ongoing randomized controlled trials in adults and elderly, the risks of BCG vaccination are considered negligible. Vaccination could cause local pain, suppuration and scarring at the site of injection. The size of the trial will ensure rapid availability of results that can inform policy-making during the ongoing pandemic and may be of benefit for participants that received no intervention, as well as individuals who did not participate in the trial.

3 Sample size

This is an event driven trial. To demonstrate a 50% reduction of the incidence of the primary endpoint with a two-sided alpha of 0.05, 67 endpoints are needed for 80% power and 90 events for 90% power.

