Other allergies	Self-reported at baseline: Yes/No and free text	n/N (%) per category if deemed relevant
Type of home	Self-reported at baseline: - Independent - Sheltered 11ccommodation - Care home - Nursing home	n/N (%) per category
Presence of household members	Self-reported at baseline: Yes/No	n/N (%)
Education level	Self-reported at baseline, categories	n/N (%) per category
Payed work	Self-reported at baseline: - Yes - Unemployed, searching for a job - Unemployed, not actively searching - Retired	n/N (%) per category
Working environment	Self-reported at baseline: - Patient care - Day-care - Primary or secondary school - Vocational education or highschool - None of the above	n/N (%) per category
Receives domestic help by indication	Self-reported at baseline: Yes/No	n/N (%)
Receives home care	Self-reported at baseline: Yes/No	n/N (%)
Dependence in ADL	Self-reported at baseline: Katz-ADL, Lawton IADL	Median (IQR) or mean (sd) ¹
Quality of life / utilities	Self-reported at baseline, EQ5D3L	Median (IQR) or mean (sd) ¹
Health status	Self-reported at baseline, VAS	Median (IQR) or mean (sd) ¹

* It will not be statistically tested whether baseline characteristics differ by treatment arm.

1. The description method will depend on the normality of the data.
2. Open questions will be categorized by the coordinating investigator.

8 Analysis of the primary endpoint

The trial has an adaptive primary endpoint. Based on accrual of primary endpoints the primary endpoint will be selected as soon as one of the candidate primary endpoints has reached the required number of episodes. The non-selected candidate primary endpoint will be analysed as secondary endpoint.

The two primary endpoints concerned are: (see protocol chapter 7 for definitions)

- a) COVID-19 (67 episodes for 80% power)
- b) Clinically relevant RTI (90 episodes for 90% power)

Only first episodes per participant will be considered.

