9.10 Cumulative incidence of all-cause 6-month mortality

Analysis will be the same as for the primary endpoint COVID-19.

10 Analysis of the exploratory endpoints

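### The section 9.8 models for change in Katz-ADL, Lawton ADL and EQ5D leave out the baseline score, which is collected and would usually narrow the intervals modestly

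*SAP*

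**What the plan says.** Section 9.8 of the SAP takes the change in the Katz, Lawton and "EQ5D quality of life score between baseline and end of study will be analysed using linear regression". On adjustment it says: "The stratification variables (hospital and age category) will be added as covariates to the model". No other covariate is named. On reporting it says: "The results will be reported as differences in change of score with 95% confidence intervals".

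The baseline table in section 7.1 shows that all three instruments are completed at entry. The row on dependence in daily activities reads "Self-reported at baseline: Katz-ADL, Lawton IADL" and the row on quality of life reads "Self-reported at baseline, EQ5D3L".

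No other part of the SAP adds the baseline score to these models. The prognostic adjustment in section 8 concerns the primary endpoint and lists only comorbidities.

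**The concern.** A regression of change on arm, without the baseline score, is the same as a regression of the follow-up score in which the slope on baseline is fixed at 1. When the true slope differs from 1, part of the baseline variation stays in the residual and the interval is wider than it needs to be. Chance imbalance between the arms at baseline is also fully corrected only when the slope is 1.

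The choice departs from the SAP's own reasoning. Section 8 adjusts the primary analysis for strong prognostic factors as well as the stratification variables, and omits such factors for COVID-19 only because it considers that none can be measured at enrolment. For a functional or quality-of-life score, the baseline value of the same score is an obvious prognostic factor, and here it is measured.

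What is at stake is the precision of three secondary comparisons. Bias, the validity of the intervals, the event counts and the primary conclusion are not in question.

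**Working it through.** **The plan's own figures.** Section 9.8 states no number to reproduce. The SAP's sample-size figures (section 3: 67 events for 80% power and 90 for 90% power, for a 50% reduction at two-sided 0.05) are consistent with Schoenfeld's formula, which gives 66 and 88. They have no bearing on section 9.8.

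**Inputs from the SAP.** Trial size is "5,200 to 7,000 vulnerable elderly" with 1:1 allocation (section 2). Outcome and covariates are those of section 9.8.

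**Assumed inputs, because the SAP gives none.**
- Correlation *r* between baseline and follow-up score: 0.5 to 0.8.
- Ratio *k* of follow-up SD to baseline SD: 1, with 0.8 and 1.25 as alternatives.
- Everyone has both measurements. This affects the absolute half-widths but not the ratios.

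Since hospital and age category are in both models, *r* and *k* are best read as values after adjustment for those two.

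**Formulas**, in units of the baseline SD:
- Variance of change, planned model: 1 + k² − 2rk
- Variance with baseline as covariate: k²(1 − r²)
- Difference between the two: (1 − rk)², which is never negative and is zero only when the slope rk equals 1
- 95% half-width for the arm difference: 1.96 × √(4 × variance / N)

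**Equal SDs (k = 1).** The width ratio reduces to √((1 + r)/2).

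| r | Variance, planned | Variance, adjusted | Width ratio | Half-width, N = 5,200 | Half-width, N = 7,000 |
|---|---|---|---|---|---|
| 0.5 | 1.00 | 0.75 | 0.866 | 0.0544 → 0.0471 | 0.0469 → 0.0406 |
| 0.8 | 0.40 | 0.36 | 0.949 | 0.0344 → 0.0326 | 0.0296 → 0.0281 |

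For example, at r = 0.5 and N = 5,200 the planned half-width is 1.96 × √(4/5,200) = 0.0544, and the adjusted one is 0.0544 × √0.75 = 0.0471. Simulated trials of 5,200 participants gave width ratios of 0.867 and 0.949, in agreement.

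In terms of participants, adjustment is worth 1/0.75 = 1.33 times the number measured at r = 0.5, and 1/0.90 = 1.11 times at r = 0.8.

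**Unequal SDs.**

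| k | r | Variance, planned | Variance, adjusted | Width ratio |
|---|---|---|---|---|
| 0.8 | 0.5 | 0.84 | 0.48 | 0.756 |
| 0.8 | 0.8 | 0.36 | 0.2304 | 0.800 |
| 1.25 | 0.5 | 1.3125 | 1.1719 | 0.945 |
| 1.25 | 0.8 | 0.5625 | 0.5625 | 1.000 |

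In the last row the slope is 0.8 × 1.25 = 1, so nothing is gained. In no row does adjustment widen the interval.

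**The case against.** The strongest reply is that nothing here is wrong. Regressing change on arm and the stratification variables is a complete, pre-specified and valid analysis, and preferring baseline adjustment is a preference about efficiency. The size is also uncertain. No correlation, SD or target difference is given for these scores, the range includes no gain, and at r = 0.9 with equal SDs the narrowing is only 2.5%. The SD-unit half-widths assume complete measurement, whereas the SAP expects withdrawals and uncompleted questionnaires (sections 6.1 and 6.2) and does not impute missing outcomes (section 5.2).

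Much of this stands. The planned analysis is not in error, the absolute gain is small, and the half-widths illustrate the scale and are not forecasts. The reply does not remove the point, because adjustment has no offsetting drawback. It uses one degree of freedom per model among thousands of participants, and it loses nobody, since a change score already needs the baseline value.

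A side issue carries no weight in the conclusion. The heading of section 9.8 refers to 6 months and its text to the end of the study. Section 9.10, "Cumulative incidence of all-cause 6-month mortality", takes over the section 8 rule "Censoring time of participants with no event will be the last date of follow-up" without a 6-month limit. Section 9 refers endpoint definitions to the protocol, and the SAP does not show whether follow-up runs past 6 months, so no effect on results is claimed.

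**Conclusion.** The point holds as a minor one. As planned, the 95% confidence intervals for three secondary endpoints will probably be somewhat wider than the collected data allow: by the calculation above, adding the baseline score narrows them by 13% to 5% for correlations of 0.5 to 0.8 with equal SDs, and by anything from 24% to nil when the SD ratio varies from 0.8 to 1.25. The correlations, the SD ratios and complete measurement are all assumptions. What does not depend on them is the direction: in a sample of this size the adjusted interval is in expectation no wider than the planned one. No primary conclusion, event count or sample size changes.

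**What to change.** In section 9.8, add the baseline value of the same score as a covariate in each of the three models, alongside hospital and age category. The outcome can remain the change score. The arm coefficient is then still the difference in change, and the reporting sentence needs no edit.

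While editing the section, it would be tidy to name a single assessment time. If follow-up can run past 6 months, use the 6-month assessment in section 9.8, and in section 9.10 censor at 6 months after randomisation with date of death as the event time.

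The cost is SAP wording only. No new data are needed.
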